Preliminary data from these studies demonstrates that osivelotor has an acceptable safety and tolerability profile in healthy volunteers and participants with SCD as further described in Section 3.2. After single doses of osivelotor, blood and plasma PK and the mean % Hb occupancy of osivelotor increased in a linear manner following a single oral dose in healthy volunteers (Study GBT021601-011). In the initial part of the GBT021601-012 study of six SCD participants, after treatment at two dose levels, 50 mg for 5 weeks and 100 mg for 3

weeks, the % Hb occupancy averaged 32.6% (range 19.7% to 41.8%) and Hb levels increased by up to 3.1 g/dL (mean increase of 2.3 g/dL). Within the same timeframe, all participants demonstrated improvements in hematologic parameters, including reticulocytes and absolute reticulocytes, lactate dehydrogenase (LDH), and indirect bilirubin (Brown, Redfern et al. 2021).

GBT021601-013 is an ongoing Phase 1, single-center, open-label study to assess the mass balance, excretion, and PK of a single oral dose of [C]-osivelotor in healthy participants.

GBT021601-014 is an ongoing Phase 1, open-label, single-dose, non-randomized, parallel group study to evaluate the PK, safety, and tolerability of osivelotor in adult participants with renal impairment.

C5351004 is a three-part, multicenter, Phase 2/3 study of orally administered osivelotor in participants with SCD. Part A will evaluate the safety, tolerability, and efficacy of 12 weeks of osivelotor in adult participants with SCD, and determined the optimal dose of 150 mg for Part B. Part B will evaluate the efficacy of 150 mg osivelotor versus placebo in adult and adolescent participants with SCD for 48 weeks. Part C is a single-arm study which will evaluate the PK and safety of single and multiple doses of open-label osivelotor administered to pediatric participants. The study is ongoing.

Participants with SCD who participated in an osivelotor clinical study may be eligible to enroll in this open-label extension study (C5351005).

A detailed description of the chemistry, pharmacology, efficacy, and safety of osivelotor is provided in the PF-07940367 Investigator's Brochure (IB) (Pfizer, 2023), which is the Single Reference Safety Document (SRSD) for this study.

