**Population-level Summary:**

- Incidence of TEAEs – absolute and relative frequency
- Changes in laboratory assessments – descriptive summary of observed values at each visit and change from baseline.
- Changes in vital signs – descriptive summary of observed values at each visit and change from baseline.

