**Endpoints:**

- TEAE
- Lab assessments
- Vital Signs

**Intercurrent Events:** NA

**Population Level Summary:** will be provided by group/dose arm (Section 5.3). Specifically,

- for continuous endpoints: Mean
- for categorical endpoints: Proportion

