**2.2.3. Study Design**

C5351005 (OLE) is designed as a multicenter, global, open-label extension study. The primary objective is to assess the long-term safety of osivelotor in participants with SCD. This study is available to eligible participants who have previously enrolled in a Pfizer-sponsored osivelotor clinical study and meet the entry criteria for this study.

Eligible participants will receive open-label osivelotor at Baseline (Day 1). It is intended that Day 1 coincides with the final visit from the originating osivelotor study. End of Treatment (EOT) assessments from the originating study will serve as Baseline assessments for this study. If Day 1 for this study is greater than 7 days from the completion of the originating study, new baseline assessments will be obtained. If during the period between Day 1 of this study and completion of the originating study no dose is received for greater than 3 consecutive days, an appropriate loading dose will be administered prior to continued maintenance dosing.

Only participants from C5351004 Part A (also referred to as the “parent study”) were enrolled into the OLE. C5351004 Part A is a study which enrolled only adult participants. There are two sets of participants rolling over from C5351004 Part A to the OLE study – (i) participants without a delayed start (Date of first dose in C5351005 – EOT date from C5351004 + 1 ≤ 42 days) and (ii) participants with a delayed start of OLE (Date of first dose in C5351005 – EOT date from C5351004 + 1 > 42 days). Each set follows a distinct schedule of assessments as outlined in the C5351005 protocol.

**3. ENDPOINTS AND BASELINE VARIABLES: DEFINITIONS AND CONVENTIONS****3.1. Primary Endpoint(s)****3.1.1. Incidence of TEAEs**

A treatment-emergent adverse event (TEAE) is defined as an AE that occurs during the effective duration of treatment defined as the time from the first dose of study drug through last dose of study drug + 56 days.

TEAEs that occur in the parent study are not counted as TEAEs in this study. In case, the start date of AE is the same date as the treatment start date and the question in the AE CRF page “Is this AE continuing from the parent study?” = “Yes”, then the event is not a TEAE,

as long as it can be confirmed that the AE in question had a start date in the parent study and no end date in the parent study.

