## 5.2. Hypotheses and Decision Rules

No formal statistical hypothesis testing will be performed in C5351005 study. All statistical analyses will be used for estimation purposes only and as such no decision rules are required. All p-values will be considered descriptive in nature and will not be used for inference.

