### 5.3.1. Analyses for Binary and Categorical Endpoints

Descriptive statistics for binary and categorical variables will be count and percentage and will be presented in the format 'n (%)'. Unless otherwise specified, the percentage in summary tables will be calculated using number of participants in the population (header N) for each dose arm as denominator.

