#### 6.1.1. Incidence of TEAEs

AEs will be mapped to system organ class (SOC) and preferred term using the Medical Dictionary for Regulatory Activities (MedDRA).

The following guidelines will be used to capture the different types of TEAEs based on the AE CRF:

- **Treatment-Related Adverse Events:** adverse events with relationship to study treatment (as recorded on the AE eCRF page, Relationship with study treatment = Related) reported by the investigator and those of unknown relationship (i.e., no answer to the question 'Relationship with study treatment').
- **Serious Adverse Events (SAE):** serious adverse events (as recorded on the AE eCRF page, Was the AE Serious = Yes).
- **Non-Serious Adverse Events:** non-serious adverse events (as recorded on the AE eCRF page, Was the AE Serious = No).
- **Adverse Events Leading to Interruption of Study Treatment:** adverse events leading to interruption of study treatment (as recorded on the AE eCRF page, Action taken with study treatment = Drug interrupted).
- **Adverse Events Leading to Dose Reduction:** adverse events leading to dose reduction (as recorded on the AE eCRF page, Action taken with study treatment = Dose Reduced).
- **Adverse Events Leading to Discontinuation of Study Treatment:** adverse events leading to discontinuation of study treatment (as recorded on the AE eCRF page, Action taken with study treatment = Drug Permanently Discontinued).
- **Adverse Events Leading to Death:** adverse event leading to death (as recorded on the AE eCRF page, Did the AE result in Death = Yes, as well as AEs of Grade 5).

TEAEs leading to study discontinuation will be derived based on the response to the following question in the AE CRF form: "Caused Study Discontinuation"

The overall incidence of TEAEs will be summarized (Section 5.3). This table includes: TEAEs (number of TEAEs and participants with TEAEs),

Number of participants with:

- TEAEs by maximum severity,
- Treatment-related TEAE,
- Treatment-related TEAE by maximum severity,
- Treatment emergent SAE,
- Treatment-related treatment emergent SAE,
- Treatment emergent non-serious AE,
- TEAEs leading to study discontinuation,
- TEAEs leading to study treatment discontinuation,

TEAEs leading to study treatment interruption,  
TEAEs leading to dose reduction,  
TEAEs leading to death.

The TEAEs will be summarized and tabulated at participant level using counts and percentages:

- TEAEs by SOC and PT
- TEAEs by SOC, PT and maximum reported severity

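### The primary TEAE tables report percentages of participants with no time base, although each participant's observation window depends on an open-ended treatment duration

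*SAP*

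**What the plan says.** SAP 6.1.1 sets out an overview table and a series of SOC/PT tables. The overview has one event count, the total number of TEAEs. Its other rows are numbers of participants. For the rest, "The TEAEs will be summarized and tabulated at participant level using counts and percentages", and a participant counts once per preferred term. SAP 5.3.1 fixes the percentage as "calculated using number of participants in the population (header N) for each dose arm as denominator". This agrees with the declared estimand: protocol 10.1.1 gives the TEAE summary as "absolute and relative frequency", and SAP 2.2.1 has "for categorical endpoints: Proportion".

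The observation window, in SAP 3.1.1, is "defined as the time from the first dose of study drug through last dose of study drug + 56 days". It therefore equals the participant's own treatment duration plus 56 days. On duration, protocol 5.1 lets treatment continue until the drug is available from another source. The synopsis says up to 252 days, but the schedules of assessments carry visits at Day 252 and beyond, and the SAP analysis windows (Appendix 1.1) run to Day 672 and on.

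No TEAE rate per unit of time, cumulative incidence or time-to-first-event summary is planned. Duration of exposure is summarised separately (SAP 6.5.4). For VOC, SAP 6.2.1 divides by participant-years and uses log participant-years as an offset, because time on treatment varies.

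**The concern.** A percentage of participants with an event is a risk over some period. When the period differs between participants and no fixed horizon is set, the percentage has no stated time frame and grows with follow-up even if the underlying rate is constant. The primary objective is long-term safety, and protocol 3.3 justifies the study by the patient-years it will add, yet the primary TEAE tables never use patient-years.

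Two readings are at risk. One compares an OLE percentage with a figure from a study of another length. The other compares columns within this study, since dose arms and delayed-start groups stand side by side (SAP 5.3) and may have been followed for different times. The documents do not show whether they were. What is at stake is interpretation only: under SAP 5.2, "All statistical analyses will be used for estimation purposes only and as such no decision rules are required".

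**Working it through.** The documents state no TEAE rate, follow-up distribution or calculated sample size, so there is no figure of the plan's to reproduce. From the documents come the 56-day tail (SAP 3.1.1), the divisor 365.25 (SAP 6.2.1), the 252-day figure (protocol synopsis), which is 36 weeks, and Weeks 24 and 84 as scheduled analysis visits (SAP Appendix 1.1). Assumed are that everyone in a column is treated equally long, that the hazard of a first event is constant, and all hazards, proportions and event counts.

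**Step 1: window length.** PY = (7w + 56)/365.25 for w weeks of treatment.
- 24 weeks: 224/365.25 = 0.613
- 36 weeks: 308/365.25 = 0.843
- 84 weeks: 644/365.25 = 1.763

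**Step 2: rate behind a given percentage.** Rate = −ln(1 − p)/PY, per 100 PY at risk.

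| Crude % | 24 weeks | 36 weeks | 84 weeks |
|---|---|---|---|
| 5% | 8.4 | 6.1 | 2.9 |
| 10% | 17.2 | 12.5 | 6.0 |

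The ratio is 308/224 = 1.38 for 24 against 36 weeks, which is within the synopsis cap, and 644/308 = 2.09 for 36 against 84 weeks.

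**Step 3: percentage at the same hazard.** Crude % = 1 − exp(−h × PY).

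| Hazard h per PY | 36 weeks | 84 weeks |
|---|---|---|
| 0.1 | 8.1% | 16.2% |
| 0.5 | 34.4% | 58.6% |
| 4 | 96.6% | 99.9% |

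The percentage doubles for an uncommon event and hardly moves for a near-universal one.

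**Step 4: can a reader repair this from other tables?** The VOC participant-years run from first dose to EOT (SAP 6.2.1) and so omit the 56-day tail. If the whole tail is observed, using them inflates a rate by 56/168 = 33%, 56/252 = 22% or 56/588 = 9.5% at 24, 36 or 84 weeks. They also keep running after a participant's first event, which lowers the rate. The two errors act in opposite directions and do not in general cancel. The planned summaries give no time at risk to first event.

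**The case against.** The strongest objection is that nothing is wrong. The tables deliver the declared summary, there is no comparator, and no decision depends on them. That is correct, and it limits the point to an improvement. The contrast with VOC is also not a contradiction, because an annualized rate needs person-time by definition.

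A second objection is that exposure is summarised in the same columns and all AEs are listed, so a reader can form an approximate rate. That holds for a rough figure. The tail inflation in step 4 is an upper bound, since participants who leave early contribute less than 56 days. It does not give a first-event rate by preferred term.

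A third objection concerns the remedy: incidence per participant-year is independent of follow-up only if the hazard is constant. This may fail here. Delayed-start participants restart on a loading dose after more than 42 days, while the others continue from the parent study. With an assumed hazard of 0.4 per PY for 24 weeks and 0.05 afterwards, 36 against 84 weeks gives crude 18.4% against 22.1% (ratio 1.20) but 25.0 against 15.0 per 100 PY (ratio 1.66). With 0.2 then 0.1, the percentage varies more (1.63 against 1.22). So neither statistic is better in every case. That stands, and it is why the rate should sit beside n (%) and not replace it.

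Finally, every magnitude above rests on assumed durations, and analysis visit windows are not evidence of actual follow-up. That also stands.

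**Conclusion.** The point holds. The plan gives the primary TEAE endpoint as percentages of participants over windows of unequal and unstated length, with no incidence per unit of time anywhere in the TEAE summaries. Under a constant hazard and uniform treatment durations within a column, the same 10% can stand for rates that differ by a factor of 1.38 (24 against 36 weeks) or 2.09 (36 against 84 weeks). The distortion matters for less common preferred terms, SAEs and discontinuations. The actual spread of follow-up, and any difference between columns, is not documented.

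The change is worth making because the objective is long-term safety and the cost is small. No conclusion of the study is invalid without it.

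**What to change.** In SAP 6.1.1 keep n (%) and add exposure-adjusted incidence:
- **Statistic:** participants with the event per 100 participant-years at risk, with an exact Poisson 95% CI.
- **Time at risk:** from first OLE dose to the earliest of the first such event, last dose + 56 days, and the study completion/discontinuation date (SAP 5.1).
- **Where:** the overview rows for any TEAE, treatment-related TEAE, treatment-emergent SAE, TEAE leading to discontinuation and TEAE leading to death; for the SOC/PT and SAE tables, the All Participants block only.
- **Onset rule, in SAP 5.4.1.4, for this denominator only:** a partial or missing onset of a CRF-confirmed TEAE is set to the earliest possible date on or after first dose.
- **Footnote:** arms are defined by the Day 1 dose, and time counts from the first OLE dose, not the first-ever osivelotor dose. SAP 2.2.3 states that only Part A participants "were enrolled into the OLE. C5351004 Part A is a study which enrolled only adult participants". On their earlier exposure, protocol 3.1 says "Part A will evaluate the safety, tolerability, and efficacy of 12 weeks of osivelotor in adult participants with SCD".

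The cost is SAP wording, one extra statistic in the overview and in one block of the SOC/PT and SAE tables, and the onset rule. The first-dose, EOT and completion dates are already used in SAP 5.1. Programming needs a separate time at risk for each row.

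The downsides are:
- The tables become somewhat wider.
- The statistic is an average rate over follow-up.
- Later dose changes are not separated.
- Intervals are wide in small arms. With assumed counts, 5 participants in 50 PY give 10.0 (3.2 to 23.3) per 100 PY, and 1 in 10 PY gives 10.0 (0.3 to 55.7).

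The onset rule has little effect: one fully missing onset among 5 events in 50 PY, with 1.763 PY removed, gives 5/(50 − 1.763) = 10.4 per 100 PY instead of 10.0.

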#### **6.1.2. Changes in laboratory assessments**

Descriptive statistics (Section 5.3) for each parameter will be presented for baseline, each evaluation post baseline, and change from baseline for each post baseline evaluation.

#### **6.1.3. Changes in vital signs**

Descriptive statistics (Section 5.3) for each will be presented for baseline, each evaluation post baseline, and change from baseline for each post baseline evaluation.

### **6.2. Secondary Endpoint(s)**

#### **6.2.1. Annualized rate of VOC**

The summary and analyses of on-treatment VOCs will include the following:

- Duration of on-treatment period (weeks)
- Total participant-years

- Total number of VOCs
- Total number of uncomplicated VOCs
- Total number of complicated VOCs and total for each type (ACS, hepatic sequestration, splenic sequestration, priapism)
- Number of participants with VOCs
- Number of VOCs per participant
- Number of uncomplicated VOCs per participant
- Number of complicated VOCs per participant
- Annualized incidence rate of VOC
- Annualized rate of VOC along with 95% CI (using Negative Binomial Model described below)

A listing of VOC data will be provided.

Multiple VOC events will be counted per participant. Both complicated and uncomplicated VOC events will be included for the calculation of the VOC rate.

**Annualized incidence rate of VOC on-treatment** will be calculated at the group level using the formula below:

$$\text{Annualized Incidence Rate of VOC on – treatment} = \frac{\text{sum of number of events on – treatment}}{\text{sum of participant years on – treatment}}$$

where participant years on-treatment for each participant = (EOT date – date of first dose of study drug+1)/365.25. EOT date is the last known treatment date from the EOT page in CRF.

#### **Annualized rate of VOC on-treatment using Negative Binomial Model**

This analysis will not be performed by group but rather by combining all participants. A negative binomial model will be fitted to model the number of VOC events. The response variable is the number of VOC events for each participant. The independent variable is dose arm (100 mg, 150 mg) and the natural log of participant years (at participant level) will be used as the offset to account for the varying lengths of participant time on-treatment or on-study. The annualized rate and corresponding 95% CI will be presented for each dose arm and overall (100 mg + 150 mg).

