## **7.3. Randomization and Blinding**

This is an open-label study. Randomization and blinding are not applicable.

As this is an open-label, long-term extension study, the sponsor may conduct unblinded reviews and/or summaries of the data during the course of the study for the purpose of safety assessment, supporting clinical development, and/or supporting regulatory review.

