### **3.4. Baseline Variables**

The following baseline variables will be summarized. No baseline variables will be used for statistical modeling.

- Demographics: age (years), sex, race, ethnicity, geographic region (North America, Sub-Saharan Africa).

Some of the following baseline data (unless mentioned otherwise) is not collected in C5351005 EDC and will be programmatically included from the parent study database and corresponding ADaM datasets:

- Baseline characteristics: weight (kg) (see Appendix 1.2), height (cm) and SCD genotype from the parent study.
- SCD history: HU use at parent study screening, L-glutamine use at parent study screening.
- VOC history

VOCs (meeting definition in Section 3.2.1) within 12 months of parent study screening visit will be summarized in the following manner:

- a) Total number of VOCs in the past 12 months prior to parent study screening visit across all participants, total participant years in the past 12 months prior to parent study screening visit, annualized incidence rate of VOC in the past 12 months prior to parent study screening visit.
- b) Number of VOCs in the past 12 months prior to parent study screening visit per participant.
- c) Number of participants experiencing at least one VOC of specified type in the 12 months prior to parent study screening visit.

The 12-month VOC summaries will be based on counting individual events over 365 days prior to parent study informed consent date (screening visit).

- SCD complications history from parent study includes (i) historical SCD complications (including episodes ongoing at parent study screening) and (ii) concurrent SCD complications (episodes ongoing at parent study screening).
- Medical History (coded using MedDRA) from parent study.

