### 6.5. Baseline and Other Summaries and Analyses

#### 6.5.1. Baseline Summaries

Demographic data, baseline characteristics, SCD history and VOC history (overall and by dose group) will be summarized using descriptive statistics (Section 5.3).

Historical SCD complications and concurrent SCD complications will be summarized.

For medical history, counts and percentages will be provided at the participant-level and any multiple occurrences in a participant for any given term will be counted only once.

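### The negative binomial model shows 100 mg and 150 mg VOC rates side by side with no account of prior VOC burden, although dose arms are not randomised here and each participant's history count is available

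*SAP*

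**What the plan says.** SAP 6.2.1 fits a negative binomial model to the number of VOCs per participant, pooling delayed and non-delayed starters. Its specification reads: "The independent variable is dose arm (100 mg, 150 mg) and the natural log of participant years", with log participant-years as the offset. It reports an annualized rate with a 95% CI for the 100 mg arm, the 150 mg arm and the two combined. No rate ratio or difference is listed.

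SAP 3.4 states: "No baseline variables will be used for statistical modeling". It gives no reason. The same section lists among the baseline summaries "Number of VOCs in the past 12 months prior to parent study screening visit per participant", counted over the 365 days before parent-study consent. SAP 6.5.1 adds that "VOC history (overall and by dose group) will be summarized using descriptive statistics".

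On allocation, Protocol 7.3 says "Randomization and blinding are not applicable". SAP 5.3 defines dose groups by the maintenance dose assigned on Day 1 of the extension. Protocol Table 13 lists staying on, raising or lowering the Part A dose on entry, with a footnote that the Part A dose is continued until the Part A analysis is complete. Protocol 5.3 allows a dose reduction on entry for tolerability problems or lack of biomarker response in the originating study.

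On purpose, SAP 5.2 says: "All statistical analyses will be used for estimation purposes only and as such no decision rules are required".

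**The concern.** SAP 6.2.1 already provides crude group-level incidence rates. The model adds dose as a regressor and prints two dose-specific rates with intervals next to each other, a layout that invites comparison.

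Arm membership is not randomised in this study and may depend on how a participant fared in the parent study. If one arm contains people who had more crises beforehand, its on-treatment rate will tend to be higher whatever the dose does. The 12-month history count is a measure of the same outcome taken before any parent-study treatment, so it is the natural first adjustment and needs no new data. As written, SAP 3.4 rules it out. An adjustment made after an imbalance had been seen would be post hoc and would contradict the SAP.

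**Working it through.** **Starting point.** There is no plan figure to reproduce. The documents state no VOC rate, dispersion, precision target or number per dose arm. Protocol 10.5 anticipates about 500 participants, and SAP 2.2.3 says only Part A adults were enrolled. Every input below is therefore an assumption.

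**1. Imbalance between arms.** Assume no dose effect, dispersion 0.7, arms of 10 to 30, and one arm with 1.5 times the underlying VOC rate. The spurious log rate ratio is ln(1.5) = 0.405. In simulation, adding the log history count removed about a quarter to nearly three quarters of it:

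- a quarter removed: 0.405 × 0.75 = 0.304, a residual ratio of exp(0.304) = 1.36;
- three quarters removed: 0.405 × 0.25 = 0.101, a residual ratio of exp(0.101) = 1.11.

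In the same runs the SD of the log rate ratio changed by about −24% to +2%, and that of an arm rate by about −17% to +1%.

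**2. Precision, analytically.** Let k be the dispersion, p the share of k that persists from the history year to the extension, μ0 the mean history count and μ1 the mean on-treatment count. Then

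- Var(log arm rate) = (1/n)(1/μ1 + k);
- after conditioning on history, k_res = k(1 − p) + kp/(1 + kpμ0);
- SE ratio for the log rate ratio (adjusted/unadjusted) = √[(1/μ1 + k_res)/(1/μ1 + k)].

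With k = 0.5, 3 VOCs per year and 1 year of follow-up (μ0 = μ1 = 3):

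- p = 1: k_res = 0.5/(1 + 1.5) = 0.20; ratio = √(0.533/0.833) = 0.80.
- p = 0.5: k_res = 0.25 + 0.25/(1 + 0.75) = 0.393; ratio = √(0.726/0.833) = 0.93.

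Over rates of 1.5 to 3 per year, k of 0.3 to 1.0, p of 50% to 100% and follow-up of 0.5 to 2 years, the ratio runs from 0.60 to 0.99. The formula ignores the cost of estimating the extra coefficient, so it cannot show a loss.

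Even at p = 1, the history count removes only (0.5 − 0.2)/0.5 = 60% of the between-person variance in this example. One year of counts is a noisy measure of propensity, which is also why step 1 shows only partial correction.

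**3. Precision, by simulation.** Equal true rates, k of 0.3 to 0.5, mean follow-up 1 year, 400 runs per setting, with and without log(history + 0.5). Ratio of the SD of the log rate ratio, adjusted to unadjusted:

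| n per arm | full persistence | 50% persistence |
|---|---|---|
| 8 | 0.89 | 0.99–1.09 |
| 15 | 0.83 | 0.99–1.00 |
| 30 | 0.81 | 0.96–0.99 |

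Up to 74 of 400 runs (18.5%) were dropped for failed fits at 8 per arm.

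**4. The quantities the SAP reports.** In the simulations of step 3, the SD of an arm rate standardised to the pooled sample was 0.91–0.94 of the unadjusted SD at full persistence and 0.97–1.05 at 50%. For the overall rate it was 0.99–1.01, so no gain.

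**5. Standardisation matters.** At full persistence with a true marginal rate of 3.0 per year, the adjusted rate read at the mean covariate was 2.55–2.63 per year. That is a different quantity from the one the SAP reports, so adjusted rates must be averaged over the pooled baseline distribution.

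**The case against.** The strongest reply is that the plan makes no comparison to be biased. It reports a rate and interval per arm, with no contrast, test or decision rule, and an unadjusted rate is a correct description of its arm. That stands: the planned estimates are not wrong, and power for a dose contrast is irrelevant here.

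Second, imbalance will be visible, because SAP 6.5.1 already shows VOC history by dose group. That also stands and lowers the stakes. But showing an imbalance does not say how the two rates should then be read, and the plan offers nothing further.

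Third, the history count may predict poorly. It predates the parent study, parent treatment and sometimes a gap of more than 42 days come in between, and SAP 5.4.1.3 imputes incomplete history dates to the first of the month or 1 January, which can move events across the 365-day boundary. Persistence well below 100% is therefore plausible, and at 50% the precision gain is about nil.

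Fourth, how Part A doses were allocated is not in these documents, and the Table 13 footnote limits dose changes on entry for a period. The real degree of imbalance cannot be judged. This stands too: what is shown is that the arms are not randomised in this study, not that they differ.

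A reader might infer that omitting the covariate necessarily widens the intervals, or that adjustment would remove the imbalance. The documents support neither. The first depends on unstated rates, dispersion, persistence and arm sizes. The second fails because one history count cannot capture every reason for dose choice or roll-over.

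**Conclusion.** The concern holds in a limited form. The negative binomial model displays two non-randomised dose arms side by side, SAP 3.4 excludes all baseline variables without a reason, and a relevant pre-treatment count is in hand. The arm rates are valid as descriptions; comparing them can mistake prior VOC burden for a dose effect.

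The main reason to adjust is imbalance, not precision. If one arm had 1.5 times the underlying rate, adjustment would bring a spurious ratio of 1.5 down to somewhere between about 1.36 and 1.11, so it helps without solving the problem. The SD of a between-arm log ratio could fall by 19% (k of 0.3 to 0.5, 30 per arm) to about 24% (k of 0.7) with highly persistent propensity. It would be about unchanged at 50% persistence, and could rise by up to 9% at 8 per arm. The overall rate is unaffected. All these sizes rest on assumed rates, dispersion, persistence and arm sizes.

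The point is minor: the endpoint is secondary, the analysis is for estimation only, and history by dose group is already reported.

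**What to change.** - Keep the unadjusted rates in SAP 6.2.1 as the main descriptive result, and state there that they are not for dose comparison.
- Add a supplementary negative binomial model with dose arm, log(VOC count in the 12 months before parent screening + 0.5) and the same offset. Report arm rates standardised to the pooled baseline distribution, with a delta-method or bootstrap 95% CI named in advance.
- Amend the SAP 3.4 sentence to allow this one exception.
- Refer from SAP 6.2.1 to the VOC history by dose group in SAP 6.5.1, so that the two are read together.

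The cost is a few sentences of SAP text, one model term and the programming of standardised rates with their intervals. No new data are needed. The downside is one more parameter, which may not be estimable in a very small arm, so the SAP should say that the adjusted model is reported only if it converges and that a failure to converge will be stated.
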